10.2 Lost to follow up

Participants who withdraw from the trial or cease to attend trial visits prior to the end of the followup period will be classed as lost to follow up.

Every effort will be made to obtain follow-up information on these patients, unless they have completely withdrawn from the trial. Participants who are not present for a scheduled visit or follow up will be contacted by their local research team by telephone or letter. If they are contactable, the local research team will ask them to make an appointment to be seen at the next available clinic. If the participant declines or cannot be contacted, the local research team will inform their GP. If the participant is alive but not compliant with the approved visit schedule, the minimum information the local research team will aim to collect is the day 28 blood sample and visit assessment.

11 Trial Intervention

The following treatments are considered as IMPs within this trial:

- AZD7442 (Combination Monoclonal Antibody Product)
- Comirnaty bivalent (Original/Omicron BA.1) (Pfizer BioNTech)
- Spikevax bivalent (Original/Omicron) (Moderna)

Comirnaty bivalent Original/Omicron BA.1 and Spikevax bivalent (Original/Omicron)vaccines are approved for use under a conditional marketing authorisation of the supply of an unlicensed vaccine; regulation 174 of the Human Medicines Regulations 2012. Both vaccines will either be obtained through local supply or ordered from the UK Health Security Agency via the clinical trials unit. The initial supply of the vaccines will be triggered by the clinical trials unit upon receipt of all necessary approvals for the site. To order further vaccines, please contact [contact].

There is no requirement for the vaccines to be labelled as IMP for this trial. Vaccine accountability will be in accordance with local Trust policy. Vaccine should be stored and prepared as specified in the Information for UK Healthcare Professionals. See the RAPID-PROTECTION Pharmacy Manual for additional information.

11.1 Dosing schedule

IMP	Dose	Route	Time point
AZD7442 (AZD8895	600 mg single dose of AZD7442	IM injection	Day 0
followed by AZD1061)	(300 mg of AZD8895 and 300 mg of AZD1061)		
Comirnaty bivalent	0.3ml containing 15 micrograms of	As per SPC	Day 28
Original/Omicron	tozinameran and 15 micrograms of		(after day 28
BA.1: Arm 1	riltozinameran, a COVID-19 mRNA Vaccine		bloods have
	(embedded in lipid nanoparticles)		been taken)
Spikevax bivalent	Spikevax: 0.5ml containing 25 micrograms of	As per SPC	Day 28
(Original/Omicron):	elasomeran and 25 micrograms of		(after day 28
Arm 2	imelasomeran, a COVID-19 mRNA Vaccine		bloods have
	(embedded in lipid nanoparticles).		been taken)

11.2 Treatment(s)

11.2.1 Comirnaty bivalent Original/Omicron BA.1

The SARS-CoV-2 vaccine BNT162b2, manufactured by Pfizer, is an mRNA vaccine that encodes trimerised SARS-CoV-2 spike glycoprotein. mRNA vaccines exploit the host's cells to make the target protein. In each dose, half of the vaccine encodes the original virus strain and the other half encodes Omicron.

One vial (2.25 mL) contains 6 doses of 0.3 mL. One dose (0.3 mL) contains 15 micrograms of tozinameran and 15 micrograms of riltozinameran, a COVID-19 mRNA vaccine (embedded in lipid nanoparticles). The vaccine is a white to off-white frozen dispersion. Vaccine should be stored and prepared as specified in the SPC.

See the RAPID-PROTECTION Pharmacy Manual for additional information.

11.2.2 Spikevax bivalent vaccine (Original/Omicron)

The Spikevax bivalent (Original/Omicron), manufactured by Moderna Biotech, is an mRNA (messenger ribonucleic acid (mRNA), vaccine which encodes for the SARS-CoV-2 spike protein. In each dose, half of the vaccine encodes the original virus strain from 2020 and the other half encodes the Omicron strain. The vaccine is supplied in multidose vials which contain 5 doses of 0.5ml each (100 doses per pack) and is a white to off white dispersion. Each dose is prepared by withdrawing 0.5ml from a vial in

a sterile 1ml or equivalent syringe as per government guidelines. Each 0.5ml dose contains 25 micrograms of elasomeran, a COVID-19 mRNA Vaccine (embedded in SM-102 lipid nanoparticles) and 25 micrograms of imelasomeran, a COVID-19 mRNA Vaccine (embedded in SM-102 lipid nanoparticles).

Spikevax bivalent (Original/Omicron) vaccine has conditional marketing authorisation from the MHRA in Great Britain (consisting of England, Scotland and Wales).

See the RAPID-PROTECTION Pharmacy Manual for additional information.

11.2.3 AZD7442

AZD7442 is a combination of two Monoclonal Antibodies (mAbs) - Tixagevimab (AZD8895) and Cilgavimab (AZD1061) which were derived from B-cells donated by convalescent patients after SARS-CoV-2 virus infection. The human monoclonal antibodies bind to distinct sites on the SARS-CoV-2 spike protein (Dong et al, 2021). The SARS-CoV-2 spike protein contains the receptor-binding domain (RBD), which enables the SARS-CoV-2 virus to bind to receptors on human cells. By targeting the RBD region of the virus's spike protein, AZD7442 block the virus's attachment to human cells to prevent infection.

11.2.4 AZD7442 Dosage, scheduling and packaging

A single 600 mg dose of AZD7442 consists of injections (divided into sequential injections for each mAb component). If a participant experiences an immediate hypersensitivity reaction after receipt of the first IM injection, but before the next IM injection, the next IM injection should not be given. For details on the treatment of anaphylactic reactions after IMP IM injections see Section 11.3.

Table 2 Investigational Products

Intervention name	AZD7442 (Tixagevimab AZD8895 + Cilgavimab AZD1061)			
Dose formulation	Liquid Product AZD7442 will be supplied as separate vials of			
	AZD8895 and AZD1061 as 150 mg colourless to slightly yellow,			
	clear to opalescent solutions for injection. The solutions			
	contain 100 mg/mL of active ingredient (AZD8895 or AZD1061)			
	in 20 mM L-histidine/L-histidine hydrochloride, 240 mM			
	sucrose, and 0.04% (w/v) polysorbate 80, at pH 6.0. The label-			
	claim volume is 1.5 mL			
Unit dose strength(s)	600 mg AZD7442 consisting of 300 mg AZD8895 and AZD1061			
	at 100 mg/mL			
Dosage level(s)	600 mg single dose of AZD7442 (300 mg of AZD8895 and 300			
	mg of AZD1061)			

Route of administration	AZD7442 IMP is comprised of 2 separate drug products,
	AZD8895 and AZD1061, to be administered as IM injections
	sequentially as per Pharmacy Manual.
Use	Experimental
Sourcing	AZD7442 (AZD8895 + AZD1061): Provided by AstraZeneca
Packaging and labelling	IMP will be provided in a glass vial. Each glass vial will be
	labelled as required per MHRA requirements.

See the RAPID-PROTECTION Pharmacy Manual for additional information.

Preparation/Handling/Storage/Accountability

- Each vial selected for dose preparation should be inspected. If there are any defects noted with the IMP, the investigator and trials unit should be notified immediately.
- The investigator or designee must confirm appropriate temperature conditions have been maintained during transit for all IMP received, and any discrepancies are reported and resolved before use of the IMP.
- Only participants enrolled in the trial may receive IMP and only authorized site staff may supply or administer IMP. All IMP must be stored in a secure, environmentally controlled, and monitored (manual or automated) area in accordance with the labelled storage conditions, with access limited to the investigator and authorized site staff.
- The investigator, institution, or the head of the medical institution (where applicable) is responsible for IMP accountability, reconciliation, and record maintenance (i.e., receipt, reconciliation, and final disposition records).
- Further guidance and information for the final disposition of unused IMPs are provided in the Pharmacy Manual or specified handling instructions.

AZD7442 Dose Preparation and Administration Instructions

Dose Preparation Steps

The 2 drug products AZD8895 and AZD1061 (comprising AZD7442), must both be administered separately to the participant in sequential order, with no participant receiving doses of AZD8895 without also receiving the matching dose of AZD1061. The dose of AZD8895 must be administered first. The dose of AZD8895 and AZD1061 for administration must be prepared by the IMP Manager or other qualified professional using aseptic technique, and who should only remove the required DP vials for participant dosing from storage. AZD8895 and AZD1061 should be administered according to standard practice procedures for IM injections. Please refer to the Pharmacy Manual for further details.

Post dose administration

An inspection of the injection site should be performed on the day of treatment as per table 3 below;

Table 3: Injection Site Inspection on Day 1

Procedure/Time after	Immediately after IMP	15 minutes
both injections have	administration	
been administered		
Visual inspection of	X	X
site		
Palpation of site	X	X
Participant will be	x	X
asked "Are you		
experiencing any		
discomfort?"		
If yes, has the feeling		X
of discomfort changed		
since you received the		
injection?		

Any AEs should be reported as per section 14

11.2.5 Dose modification for toxicity

The IMP will be administered as described in Section 11 and the Pharmacy Manual. Dose modification is not permitted.

11.3 Management of toxicity and hypersensitivity reactions

Table 4: An Approach to Management of Anaphylactic, Hypersensitivity, and Post-injection Reactions

Severity of symptoms	Treatment	Investigational product
Mild local reactions (During	Evaluate participant, including	Pause or hold additional IMP
and post injection and	close monitoring of vital signs.	injection immediately. At the
hypersensitivity) Mild injection	At the discretion of the	discretion of the Investigator,

Centre for Trials Research Canolfan

site reactions such as redness, mild swelling, pain at the injection site or headache, nausea, non-pruritic rash, or mild hypersensitivity reactions including localised at the	Investigator, treat participant, for example, with: Localized cold pack or heat to the injection site. If more generalized reaction: • Diphenhydramine 50 mg PO or	resume current IMP administration under observation.
injection site or generalized cutaneous reactions such as mild pruritus, flushing, rash, dizziness, headache, ≤ 20 mmHg change in systolic BP from pre-administration measurement.	equivalent and/or • Acetaminophen 500 to 650 mg or equivalent dose of paracetamol and/or • Topical antihistamines and/or low- potency topical corticosteroid preparations and/or • Anti- nausea medication, as needed.	
Moderate reactions (during or immediately post injection) Injection site reaction such as those listed above under mild reactions but excluding moderate hypersensitivity reactions (see below).	Evaluate participant, including close monitoring of vital signs. Treat participant, for example, with: • Normal saline (~500 to 1000 mL/hour IV) • and/or • Diphenhydramine 50 mg IV or equivalent and/or • Acetaminophen 500 to 650 mg or equivalent dose of paracetamol and/or • Anti- nausea and/or antiemetic intramuscular, as needed.	Stop or hold additional IMP administration immediately. At the discretion of the Investigator, resume current IMP administration under observation.
Severe Above plus fever with rigors, hypo- or hypertension with ≥40 mmHg change in systolic BP, signs of end-organ dysfunction (eg, symptomatic hypotension such as hypotonia, syncope, incontinence, seizure) from pre-infusion measurement, or wheezing, angioedema, or stridor OR Life-threatening (Defined as a reaction that is life-threatening	Evaluate participant, including close monitoring of vital signs. Maintain airway, oxygen if available. Treat participant immediately, for example with: • Normal saline (~500 to 1000 mL/hour IV) Epinephrine for bronchospasm, hypotension unresponsive to IV fluids, or angioedema. Dose and route as per local SOC, example, epinephrine 1:1000, 0.5 to 1.0	Stop IMP administration immediately. Do not resume current dosing. Permanently discontinue IMP administration. Consider need for additional oral antihistamine administration or oral corticosteroid administration to prevent reoccurrence of symptoms over subsequent 2 to 3 days.

	Г	
and requires pressor and/or	mL administered SC for mild	
ventilator support or shock	cases and intramuscular for	
associated with academia and	more severe cases	
impairing vital organ function due to tissue hypoperfusion)	IV corticosteroids, such as hydrocortisone	
	100 mg or methylprednisolone	
	20 to 40 mg	
	Diphenhydramine 50 mg IV or	
	equivalent • Acetaminophen	
	500 to 650 mg or equivalent	
	dose of paracetamol	
	Grade 3 wheezing,	
	hypotension or angioedema is	
	unresponsive to single dose of	
	epinephrine	
	epinepinine	
	Grade 4 event at the discretion	
	of the investigator	
	_	

11.4 Overdose

For this trial, any dose of AZD7442 > 300 mg of either individual mAb will be considered an overdose. There is no recommend specific treatment for an overdose. Symptoms of overdose should be treated as per clinical judgement.

- An overdose with associated AEs is recorded as the AE diagnosis/symptoms on the relevant AE modules in the eCRF and on the Overdose eCRF module.
- An overdose without associated symptoms is only reported on the Overdose eCRF module. If an overdose of AZD7442 occurs in the course of the trial, then the PI or other site personnel inform appropriate trial representative immediately, but no later than 24 hours of when he or she becomes aware of it.

The designated trial representative works with the PI to ensure that all relevant information is provided to the data entry site within 1 or 5 days for SAEs, and within 30 days for other overdoses.

Any overdose of Pfizer BioNTech (BNT162b2) and the Moderna (mRNA-1273) vaccines should be managed according to the SPC and local clinical practice protocols.

11.5 Pre-medication

No pre-medications are required before treatment with AZD7442, Spikevax bivalent (Original/Omicron) and Comirnaty bivalent (Original/Omicron BA.1).

11.6 Permitted, Restricted, and Prohibited Medications

Permitted, restricted, and prohibited medications are summarized in Table 5. Any medication or vaccine (including over-the-counter or prescription medicines, vitamins, and/or herbal supplements) that the participant is receiving at the time of enrolment or receives during the trial must be recorded, along with:

- Reason for use
- Dates of administration, including start and end dates
- Dosage information, including dose and frequency

The Trial Physician should be contacted if there are any questions regarding concomitant or prior therapy

Use Category	Type of medication/treatment	Timeline/instructions
Permitted	Routine Vaccines	Licensed influenza vaccines are permitted at any time. All other routine non-COVID vaccines are permitted beginning > 30 days after IMP dose with the exception of patients receiving a haemopoietic stem cell transplant who may receive non-COVID vaccines at any time.
	Allergen immunotherapy	Allowed if participant has been receiving stable therapy for at least 30 days prior to Visit 1 and there is no anticipated change during the treatment period. Allergen immunotherapy should not be administered on the same day as IMP

Table 5: Permitted, restricted and prohibited medications

Centre for Trials Research Canolfan

	Commercial biologics,	Allowed, provided the
	prednisone,	participant is stable on
	immunosuppressive	maintenance dose (at steady
	medications (e.g., azathioprine,	state) prior to Visit 1, and must
	tacrolimus, cyclosporine,	not be administered on the
	methotrexate, or cytotoxic	same day as IMP
	chemotherapy,	
	immunotherapy or targeted	
	treatment for cancer)	
		tant medications prescribed by
		ospital team for management of nd/or for health maintenance.
		hospital providers, or where
		hould prescribe appropriate
		eatments deemed necessary to
		and comfort during the trial.
		-19 after receiving IMP should be
	treated according to local	standard of care, including
	investigational agents within a c	linical trial setting.
Prohibited	Not applicable	Not applicable
Restricted	Contraceptive methods	See section 14.8
	Blood/plasma donation	Participants must abstain from
		donating blood or plasma from
		the time of informed consent
		and for 5 half-lives after dose of
		study drug, i.e. one year.
	Standard of care COVID-19	Participants must not obtain
	vaccines	standard of care approved
		COVID-19 boosters until at
		least 3 months after receiving
		their vaccine booster on this
		study unless the study team specifically advise otherwise.

11.6.1 **Trial restrictions- contraception**

Participants must follow the contraception requirements outlined in section 14.8.

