8.1 Inclusion criteria

The participant must satisfy the following criteria to be eligible for the trial:

All participants

- 1. Provide written informed consent.
- 2. Previously completed SARS-CoV-2 vaccinations given as part of standard care at the time of enrolment.
- 3. Able and willing (in the Investigator's opinion) to comply with all trial requirements.
- 4. Willingness to practice continuous effective contraception during the first 3 months of the trial and, if appropriate, a negative pregnancy test on the day of screening.
- 5. Provide access to all medical records with respect to current and past medical treatments.
- 6. Have one or more of the following eligible conditions.

7. Adults ≥18 years

Eligible Conditions

Cohort 1: Haematological malignancies

Patients with a diagnosis of haematological malignancies and receiving one the following treatments:

- Cohort 1a Patients receiving active therapy with immunosuppressive or immunomodulating agents including:
 - B-cell targeted therapies (rituximab or other anti-B-cell Ab therapy) used either as monotherapy or in combination with cytotoxic therapy in lymphoma / chronic lymphoproliferative disorders

OR

• JAK inhibitors (ruxolitinib or equivalent) in myeloproliferative neoplasms (MPNs)

OR

• ImiD drugs (thalidomide, lenalidomide, pomalidomide or equivalent) in myeloma and other plasma cell dyscrasias

OR

• BTK inhibitors (ibrutinib or equivalent) in chronic lymphocytic leukaemia / chronic lymphoproliferative disorders

OR

- Treatment within 24 months with lymphodepleting agents followed by chimaeric antigen receptor (CAR) T-cell therapy for any haematological malignancy
- Cohort 1b Patients receiving aggressive therapy expected to cause temporary ablation of immune function including:
 - Acute leukaemia (AML or ALL) being treated with curative intent using intensive combination chemotherapy schedules (excluding acute promyelocytic leukaemia)

OR

• Patients within 24 months of receipt of allogeneic stem cell transplant or receiving systemic immunosuppression for graft versus host disease.

Cohort 2: Solid Tumours

• Early (Cohort 2a) or advanced cancer (Cohort 2b) (solid organ) undergoing systemic cancer treatment. Hormone treatments given alone such as tamoxifen or an aromatase inhibitor or LHRH agonist for early or advanced breast and prostate cancer are not considered to be a systemic treatment.

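### Table 5 permits background immunosuppression and cancer therapy only at a steady-state dose and not on the IMP day, which conflicts with treatments that section 8.1 recruits patients for

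*Protocol*

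**What the plan says.** One row of Table 5 (Protocol section 11.6), in the permitted category, groups commercial biologics, prednisone, immunosuppressants (azathioprine, tacrolimus, cyclosporine and methotrexate are named), cytotoxic chemotherapy, immunotherapy and targeted cancer treatment. These are allowed if the participant is stable on a "maintenance dose (at steady" "state) prior to Visit 1, and must" not be given them on the same day as IMP.

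Section 8.1 recruits patients because they receive drugs of these kinds:

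- Cohort 1b is headed "Patients receiving aggressive therapy expected to cause temporary ablation of immune function including", and its first entry is "Acute leukaemia (AML or ALL) being treated with curative intent using intensive combination chemotherapy schedules". Its second entry includes patients "receiving systemic immunosuppression for graft versus host disease".
- Cohort 1a includes "JAK inhibitors (ruxolitinib or equivalent) in myeloproliferative neoplasms (MPNs"), "ImiD drugs (thalidomide, lenalidomide, pomalidomide or equivalent) in myeloma and other plasma cell dyscrasias" and "BTK inhibitors (ibrutinib or equivalent) in chronic lymphocytic leukaemia / chronic lymphoproliferative disorders".
- Cohort 2 takes patients with solid tumours on systemic treatment and counts them as eligible after a dose within 42 days of trial entry.
- Cohorts 3a and 4 include transplant recipients and patients with kidney or inflammatory disease who are on immunosuppression.

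Section 8.1 does not require a stable or maintenance dose for any of these cohorts. Section 18 requires the Principal Investigator to report any non-compliance with the protocol.

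**The concern.** The row governs the background treatment that makes these patients worth studying, yet its conditions do not fit some of that treatment. A site that follows section 8.1 can enrol a patient who fails the row from the start. A site that follows the row to the letter may withhold a day of immunosuppression or targeted therapy from someone who needs it continuously, such as a transplant recipient on tacrolimus. If the site carries on treating, it has a deviation to report for giving the patient's normal care. Sites may settle this differently, so therapy interruptions and deviation logs could vary between sites for no clinical reason.

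**Working it through.** No arithmetic applies. The check sets Table 5 beside section 8.1, one condition at a time.

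**Steady-state condition**

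1. The row names cytotoxic chemotherapy, so chemotherapy falls under the condition.
2. Cohort 1b admits patients on intensive, curative-intent combination chemotherapy for AML or ALL, and its own heading says that the therapy is expected to ablate immune function temporarily. Such treatment is not a maintenance dose at steady state. These patients meet section 8.1 and fail the row.
3. Cohort 2 needs only one systemic dose in the 42 days before entry. A patient who has had a first dose and no more is eligible, but is not yet stable on a maintenance dose. This patient also meets section 8.1 and fails the row.
4. The schedule in Table 6 names its visits Baseline and Day 0 to Day 180, and does not use the label Visit 1. Whether Visit 1 means baseline or Day 0, steps 2 and 3 come out the same.

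This conflict follows from the protocol's wording and needs no information on dosing frequency.

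**Same-day condition**

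1. AZD7442 is given on Day 0 (section 11.1), and the row bars the listed drugs on the day of IMP.
2. The protocol gives no dosing frequencies, so daily intake is an assumption. The row itself names tacrolimus, cyclosporine and prednisone. The same reasoning covers any JAK inhibitor, BTK inhibitor, ImiD or other immunosuppressant in section 8.1 that is taken daily.
3. For a drug taken daily, no Day 0 can be chosen on which the drug is not due. Compliance then means leaving out that day's treatment.
4. For an agent given at intervals, such as an infusion, Day 0 can be placed on another day and there is no conflict. Section 13 asks for trial visits to coincide with routine visits, but only where possible.

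**Search for an exemption**

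- Table 5 does write exceptions into its rows: the routine-vaccine row excepts haemopoietic stem cell transplant patients. The row at issue contains none.
- The prohibited category is marked not applicable. That does not remove conditions attached to a permitted category.
- The Trial Physician may be asked about concomitant therapy. That is a route for questions and waives nothing.
- The next row, on medication prescribed by the hospital team, has lost its left edge in the text available. The legible part reads as a general permission to prescribe needed treatment, and it lifts neither condition.

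**The case against.** The strongest reply is that the damaged row directly below is where a carve-out would naturally sit, and what survives of it points towards letting the treating team prescribe what the patient needs. This stands as a limit: the point can say only that no exemption is legible. Anyone with the intact table should read that row first. Even so, a general permission to prescribe would sit awkwardly beside two specific conditions on named drugs, unless it expressly overrode them.

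It can also be said that the row was evidently written to allow this population's drugs, that no text tells a site to interrupt therapy, and that withholding a dose is an unlikely reading. The intention is probably as described, but the wording does not carry it out. The reply that the same-day limb needs pharmacology from outside the document is fair, and that limb is therefore conditional. An eligibility rule and a concomitant-medication rule can apply together, so silence in section 8.1 is not in itself a contradiction. For AML/ALL chemotherapy and the first-dose cancer patient, however, section 8.1 positively admits what the row does not allow.

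Three stronger inferences are tempting and are not supported:

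- **That the row shuts out cohort 1b or part of cohort 2.** Section 8 sets eligibility by the inclusion and exclusion criteria alone, so no cohort is formally excluded.
- **That the results would be biased.** Section 15.7 includes all enrolled participants and section 16 takes a treatment-policy approach to intercurrent events, so no analysis bias follows from deviations on this row.
- **That a second day's treatment must be missed at the booster visit.** Section 11 lists the boosters as IMPs, but section 11.2.4 uses the term for AZD7442. Whether the row reaches Day 28 is unclear.

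**Conclusion.** The point holds as a minor wording conflict. The steady-state condition contradicts section 8.1 for AML/ALL patients on intensive chemotherapy and for cohort 2 patients who have had only a first dose. The same-day condition conflicts with any qualifying drug that is taken daily, on the assumption of daily intake. For such a participant the cost of literal compliance is one omitted day of treatment, on Day 0. The protocol gives no breakdown of background drugs, so no share of participants is claimed.

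Recruitment was paused at the beginning of April 2023 (section 13.1.1). What remains is the safety of participants if dosing resumes, and consistent classification of deviations in those already treated. The conclusion also rests on the cut row holding no express exemption.

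**What to change.** Reword the one row in Table 5:

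1. Exempt background therapy that qualifies a patient for a cohort from the steady-state condition.
2. Limit the same-day condition to parenteral agents that can be scheduled on another day.
3. State that continuous oral immunosuppressive or targeted therapy is not to be interrupted for trial dosing.

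As a clarification, the row could also say whether IMP there means AZD7442 only or the boosters too.

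The cost is a wording amendment, with no extra patients, visits or procedures. Under section 21.2 a substantial amendment needs approval by the ethics committee and, where applicable, the MHRA before it takes effect, and a minor one does not need prior approval. The downside is slightly less separation between background drugs and IMP when a reaction on the dosing day has to be attributed.
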